2.6.2.2 Adverse events of special interest / grouping of AEs

An adverse event of special interest is a grouping of adverse events that are of scientific and medical concern specific to compound sabatolimab. These groupings are defined using MedDRA terms, SMQs (standardized MedDRA queries), HGLTs (high level group terms), HLT (high level terms) and PTs (preferred terms). Customized SMQs (Novartis MedDRA queries, NMQ) may also be used. A NMQ is a customized group of search terms which defines a medical concept for which there is no official SMQ available or the available SMQ does not completely fit the need. It may include a combination of single terms and/or an existing SMQ, narrow or broad. These searches will be defined in the eCRS (electronic Case Retrieval Strategy) in the DMS (Document Management System) and a listing of search terms will be provided in the CSR.

For each specified AESI, the number (%) of participants with at least one event of the AESI occurring during on treatment period will be summarized together with the individual preferred terms in that grouping. In addition, number (%) of participants with at least one AESIs by maximum CTC grade, related AESIs, serious AESIs as well as action taken and outcome of the respective AESI will be summarized.

2.6.2.3 Deaths

Separate summaries for on-treatment and all deaths (including post-treatment deaths not in the AE CRF but in the survival CRF) will be produced showing reasons for deaths by the primary reason and PT. All deaths will be listed, post treatment deaths will be flagged. A separate listing of deaths prior to starting treatment will be provided for all screened participants.

2.6.2.4 Laboratory data

Grading of laboratory values will be assigned programmatically as per National Cancer Institute (NCI) Common Terminology Criteria for Adverse Events (CTCAE) version 5.0. The

calculation of CTCAE grades will be based on the observed laboratory values only, clinical assessments will not be taken into account.

CTCAE Grade 0 will be assigned for all non-missing values not graded as 1 or higher.

For laboratory tests where grades are not defined by CTCAE version 5.0, results will be categorized as low/normal/high based on laboratory normal ranges.

For laboratory tests where grades are defined by CTCAE v5.0:

• Shift tables using CTCAE v5.0 grades to compare baseline to the worst on-treatment value

Liver function parameters of interest are total bilirubin, ALT, AST and alkaline phosphatase. The number (%) of participants with the worst post-baseline values as per Novartis Liver Toxicity guidelines will be summarized.

All CTCAE grade 3 or 4 laboratory toxicities will be listed.

2.6.2.5 Other safety data

Safety data listed in this section will be analyzed and summarized for the safety set and presented by dose level of sabatolimab (400 mg Q4W, 800 mg Q4W) and for all participants ("All participants" column), and by visit/sampling time point.

2.6.2.6 ECG and cardiac imaging data

ECGs are collected as 12-lead triplicate using the ECG machines supplied by the central laboratory and then transmitted electronically to the central laboratory for central review by an independent reviewer. These central ECGs are done at screening, C1D1 pre-dose, C1D8 post-dose, C3D8 post-dose and at end of treatment; however, additional ECGs can be done if clinically indicated.

Notable ECG values during on-treatment period in participants with normal values at baseline (for the respective QTc value) will be summarized using the following criteria:

ECG parameter (unit)	Clinically notable criteria
QTcF (ms)	Increase >30 and <=60 ms
	Increase >60 ms
	New >450 to <=480 ms
	New >480 to <=500 ms
	New >500 ms
HR (bpm)	Increase >25% and HR >100 bpm
	Decrease >25% and HR<50 bpm
PR (ms)	Increase from baseline >25% and to a value > 200 ms
	New value of > 200 ms
QRS (ms)	Increase from baseline >25% and to a value > 120 ms
	New values of QRS > 120 ms

Table 2-3Notable ECG values

Novartis	For business use only	Page 35 of 46
Statistical Analysis Plan (SAP)		MBG453B12203
· · · · ·		

In addition, local ECGs are performed but not used for summary of QTc values. If abnormalities are observed based on these local ECGs, these abnormalities are to be reported and thus summarized as AEs.

2.6.2.7 Vital signs

Notable vital sign values during on-treatment period will be summarized using the following criteria:

Vital sign (unit)	Clinically notable criteria	
	above normal value	below normal value
Systolic blood pressure (mmHg)	>= 180 with increase from baseline of >= 20	<= 90 with decrease from baseline of >= 20
Diastolic blood pressure (mmHg)	>= 105 with increase from baseline of >= 15	<= 50 with decrease from baseline of >= 15
Pulse rate (bpm)	>= 100 with increase from baseline of > 25%	<= 50 with decrease from baseline of > 25%
Weight (kg)	Increase >= 10% from baseline	Decrease >= 10% from baseline
Body temperature (°C)	>= 39.1	

Table 2-4 Notable vital sign valu

2.6.3 Pharmacokinetic

2.6.3.1 Sabatolimab and venetoclax drug concentrations

Pharmacokinetic analyses will be summarized for the sabatolimab or venetoclax pharmacokinetic analysis set. Sabatolimab and venetoclax concentration data will be listed by participant, and visit/sampling time point. Descriptive summary statistics for sabatolimab and venetoclax concentrations will be provided by the dose level of sabatolimab, visit/sampling time point. Concentrations at EOT, 30-day safety follow-up and 150-day safety follow-up visit will not be included in the summary table for sabatolimab. In the case of predose samples, the actual dose would reflect the prior dose the participant received. The summary table for venetoclax concentration data only includes the patients whose prior dose (D7 dose) was 400 mg at each sampling time point. Summary statistics will include mean (arithmetic and geometric), SD, CV (arithmetic and geometric), median, minimum, and maximum, as well as the frequency (n, %) of concentrations below the lower limit of quantification (LLOQ) and reported as zero. Values below the LLOQ will be treated as missing for the calculation of the geometric means and geometric CV%. Sabatolimab and venetoclax concentration data obtained from samples collected outside of PK sample collection window as defined per protocol will be flagged and excluded for the summary statistics. PK parameters (the minimum observed plasma or serum drug concentration (Cmin or Ctrough) and the maximum (peak) observed plasma or serum drug concentration (Cmax)) will be estimated and reported. Missing values for any PK parameters or concentrations will not be imputed and will be treated as missing.

All concentration data for sabatolimab vs. time profiles with median will be displayed graphically, excluding concentrations at EOT, 30-day safety follow-up and 150-day safety follow-up visit. All concentration data for venetoclax by timepoints will be displayed graphically. The concentrations collected before dose administration on Day 8 of Cycle 3 and beyond are Ctrough for sabatolimab. If the sabatolimab pre-dose sample is collected more than +/- 3 days from the 28 day dose cycle, this concentration would be removed from the graph and summary. If the venetoclax pre-dose sample is collected more than +/- 3 hours from the 24 hours daily dose interval after the prior dose on Day 7, this concentration would be removed from the graph and summary. End of infusion concentration will be reported as Cmax.

2.6.3.2 As the half-life of venetoclax is approximately 26 hours, the sample collected at Cycle 1 Day 8 will be considered as the venetoclax trough concentration at steady state before any dose administration of sabatolimab.Population pharmacokinetic analysis

If data permit, a mixed-effects model may be applied to the serum sabatolimab concentrationtime data from this study along with other studies to generate post-hoc estimates of pharmacokinetic parameters using appropriate software to characterize sabatolimab exposure and to determine the effects of intrinsic (i.e. demographic factors) and extrinsic covariates (e.g. combination partners) on sabatolimab exposure.

The population pharmacokinetic analyses will not be conducted for the abbreviated final CSR. If there are sufficient data for analysis, the details of the population pharmacokinetic analyses may be provided in a separate reporting and analysis plan, and the results may be reported in a separate population pharmacokinetic report.

2.6.4 Immunogenicity

2.6.4.1 Sample ADA Status

Each IG sample is assessed in a three-tiered anti-drug anti-body (ADA) testing approach. All IG samples are analyzed in the initial screening assay (first tier). Samples testing negative in the screening assay are not subject to a confirmatory assay. Samples testing positive in the screening assay are then subjected to the confirmatory assay to demonstrate that ADA are specific for the therapeutic protein product (second tier). The titer of confirmatory positive samples will be subsequently determined in the titration assay (third tier). Samples identified as positive in the confirmatory assay are considered ADA positive. Samples can test negative in either the screening or confirmatory assay but for analysis purposes they are not differentiated. The following properties of each sample will be provided in the source data:

- Result of the assay according to a pre-specified confirmatory cut point: ADA positive (yes) or ADA negative (no)
- Titer (for positive samples): numerical representation of the magnitude of ADA response.
- When titer values are below the titer cut point with minimal required dilution (MRD) and the result is reported as 'Titer value 50 (MRD)', it is interpreted as a POSTIVE sample with titer equal to 50. Drug tolerance level: highest drug concentration that does not interfere with the ADA detection method

• Fold titer change (i.e. x-fold): threshold for determining treatment boosted

Determinant samples are defined as samples which are not unevaluable (where unevaluable = sample where assay is not available).

The following definitions apply only to determinant samples:

- ADA-negative sample: Determinant sample where the assay is ADA negative and MBG453 PK concentration at the time of IG sample collection is less than the drug tolerance level.
- ADA-positive sample: Determinant sample where the assay is ADA positive.
- ADA-inconclusive sample: Sample where assay is the ADA is negative and MBG453 PK concentration at the time of the IG sample collection is greater than or equal to the drug tolerance level or missing

The following definitions apply only to post-baseline ADA-positive samples with a corresponding determinant baseline sample. To be classified as treatment-boosted or treatment-unaffected, both the post-baseline and baseline titer must be non-missing:

- treatment-induced ADA-positive sample: ADA-positive sample post-baseline with ADAnegative sample at baseline.
- treatment-boosted ADA-positive sample: ADA-positive sample post-baseline with a titer that is at least the fold titer change greater than the ADA-positive baseline titer.
- treatment-unaffected ADA-positive sample: ADA-positive sample post-baseline with a titer that is less than the fold titer change greater than the ADA-positive baseline titer.

NOTE: PK concentrations which are flagged for exclusion will still be used to determine ADA-inconclusive and ADA-negative samples.

Listings will be provided of sample ADA status (including titer for positive samples).

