5.2 Exclusion criteria

Participants meeting any of the following criteria are not eligible for inclusion in this study.

- 1. Prior exposure to TIM-3 directed therapy or any BCL-2 inhibitor (including venetoclax) at any time.
- 2. Prior therapy with immune check point inhibitors (e.g. anti-CTLA4, anti-PD-1, anti-PD-L1, or anti-PD-L2) or cancer vaccines is not allowed if the last dose of the drug was administered within 4 months prior to start of treatment.
- 3. Previous first-line treatment for very high risk or high risk myelodysplastic syndromes (based on IPSS-R, Greenberg et al 2012 and Arber et al, 2016) with any antineoplastic agents, approved or investigational, including chemotherapy, lenalidomide and hypomethylating agents (HMAs) such as decitabine or azacitidine.

However, a single cycle of HMAs treatment only started prior to enrollment is allowed.

- 4. Live vaccine administered within 30 days prior to start of treatment
- 5. Current use or use within 14 days prior to start of treatment of systemic steroid therapy (> 10mg/day prednisone or equivalent) or any immunosuppressive therapy. Topical, inhaled, nasal, ophthalmic steroids are allowed. Replacement therapy, steroids given in the context of a transfusion are allowed and not considered a form of systemic treatment
- 6. History of severe hypersensitivity reactions to any ingredient of study drug(s) (azacitidine, venetoclax or sabatolimab) or monoclonal antibodies (mAbs) and/or their excipients
- 7. Participants with myelodysplastic syndrome (MDS) based on 2016 WHO classification (Arber et al, 2016) with revised International Prognostic Scoring System (IPSS-R) \leq 4.5
- 8. Diagnosis of acute myeloid leukemia (AML) including acute promyelocytic leukemia and extra-medullary acute myeloid leukemia based on WHO 2016 classification (Arber et al, 2016)
- 9. Diagnosis of therapy-related MDS based on WHO 2016 classification (Arber et al, 2016)
- 10. Diagnosis of chronic myelomonocytic leukemia (CMML), MDS/MPN or primary or secondary myelofibrosis based on 2016 WHO classification (Arber et al, 2016)
- 11. History of organ transplant or allogenic hematopoietic stem cell transplant
- 12. Any concurrent severe and/or uncontrolled medical condition e.g., any active systemic infection, or any severe and/or uncontrolled infection requiring parenteral anti-infectives

including antibacterial, antiviral or antifungal therapy (such as severe pneumonia, meningitis, or septicemia)

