2.6.4.2 Participant ADA status

Any IG sample collected after 150 days of the last dose of sabatolimab will not be used for summaries or derivations and will only be included in the listing.

Participant ADA status is defined as follows:

- Treatment-induced ADA-positive participant: participant with ADA-negative sample at baseline and at least one treatment-induced ADA-positive sample.
- Treatment-boosted ADA-positive participant: participant with ADA-positive sample at baseline and at least one treatment-boosted ADA-positive sample.
- Treatment-unaffected ADA-positive participant: participant with ADA-positive sample at baseline, no treatment-boosted ADA-positive samples, and at least one treatment-unaffected ADA-positive sample.
- Treatment-reduced ADA-positive participant: participant with ADA-positive sample at baseline and at least one post baseline determinant sample, all of which are ADA-negative samples.

- ADA-negative participant: participant with ADA-negative sample at baseline and at least one post baseline determinant sample, all of which are ADA-negative samples.
- Inconclusive participant: participant who does not qualify as treatment-induced ADA-positive, treatment-boosted ADA-positive, treatment-unaffected ADA-positive, treatment-reduced ADA-positive, or ADA-negative.

Listings will be provided of participant ADA status.

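### A negative ADA sample taken before the first sabatolimab dose is classed as inconclusive if its PK value is missing, although no drug can be present to interfere

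*SAP*

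**What the plan says.** SAP 2.6.4.1 sorts assay-negative samples by the sabatolimab concentration at the time of sampling. A sample is ADA-negative only if the "PK concentration at the time of IG sample collection is less than the drug tolerance level". It is ADA-inconclusive if that concentration "is greater than or equal to the drug tolerance level or missing". The same section describes the drug tolerance level as the highest concentration that leaves the ADA assay undisturbed.

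The later classes depend on the baseline sample. The sample definition reads "treatment-induced ADA-positive sample: ADA-positive sample post-baseline with ADAnegative sample at baseline". In SAP 2.6.4.2 a treatment-induced participant is a "participant with ADA-negative sample at baseline and at least one treatment-induced ADA-positive sample", and an ADA-negative participant also needs an ADA-negative baseline sample. Whoever fits no class falls into the residual one: "Inconclusive participant: participant who does not qualify as treatment-induced ADA-positive", nor for any of the other named classes.

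Two further statements bear on missing PK. SAP 2.6.3.1 says "Missing values for any PK parameters or concentrations will not be imputed and will be treated as missing". A note in SAP 2.6.4.1 says "PK concentrations which are flagged for exclusion will still be used to determine ADA-inconclusive and ADA-negative samples".

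On drug exposure, Protocol 5.2 (criterion 1) excludes "Prior exposure to TIM-3 directed therapy or any BCL-2 inhibitor (including venetoclax) at any time". Protocol 6.1.1 gives sabatolimab on Day 8 of each cycle. In Protocol Table 8-9 the first time point marked for both PK and IG is Cycle 1 Day 8, before the infusion.

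**The concern.** The inconclusive class guards against one problem: circulating sabatolimab can hide antibodies, so a negative assay cannot be trusted when drug is present at an interfering level or its level is unknown. Before the first infusion the level is known without measurement. A missing PK result at that time adds no uncertainty to a negative assay, yet the rule treats it as though it did.

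The cost falls on the baseline. Without an ADA-negative baseline, a participant who later develops antibodies cannot be called treatment-induced, and one who never does cannot be called ADA-negative. ADA incidence on treatment is a secondary endpoint by dose level (SAP Table 1-1). SAP 1.2 drops only the fatigue objective, so immunogenicity will still be reported, in cohorts planned at about 6 and 12.

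**Working it through.** The documents give no figure for ADA incidence, so there is none to reproduce. The check is to apply the definitions and see which statuses change.

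**Step 1. Is there a rescue elsewhere?** No. Missing PK is not imputed (SAP 2.6.3.1). The note in 2.6.4.1 restores PK values flagged for exclusion, not absent ones.

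**Step 2. Apply the rules** to a participant whose pre-first-dose assay is negative, taking that sample as baseline:

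| Pre-dose PK | Later samples | Status under the SAP | Status if the pre-dose sample counts as negative |
|---|---|---|---|
| Measured, zero | a positive | treatment-induced | treatment-induced |
| Measured, zero | all negative | ADA-negative | ADA-negative |
| Missing | a positive | Inconclusive | treatment-induced |
| Missing | all negative | Inconclusive | ADA-negative |

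Only the missing PK value separates the first two rows from the last two. In the third row the baseline sample still counts as determinant, because its assay result exists. The later positive sample is therefore within the scope of the sample definitions, yet it is neither treatment-induced, boosted nor unaffected.

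**Step 3. Which participants keep the same status either way?**
- Baseline assay positive: this class needs no PK value.
- No post-baseline determinant sample: Inconclusive either way.
- No later positive sample, but at least one later inconclusive sample: Inconclusive either way, because ADA-negative status requires every later determinant sample to be ADA-negative.

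**Step 4. When is the PK value truly missing?** Sabatolimab concentrations below the quantification limit are reported as zero; they are treated as missing only for geometric means and geometric CV (SAP 2.6.3.1). A measured pre-dose value below that limit therefore passes. PK and IG share the same time point, with a single blood sample at each (Protocol 8.5.2.1). What remains is a valid IG result with no PK result from the same visit.

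**Step 5. Size, as an illustration.** Assume that incidence counts treatment-induced participants, that the planned cohort sizes hold (SAP 2.9.1), and that one such case is lost.
- Cohort of 12, one true case: 1/12 = 8.3% becomes 0%.
- Cohort of 6, one true case: 1/6 = 16.7% becomes 0%.
- Cohort of 12, two true cases: 2/12 = 16.7% becomes 1/12 = 8.3% if the participant stays in the denominator, or 1/11 = 9.1% if not.

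A lost true negative can push the other way: with one case in 12, removing a true negative from the denominator gives 1/11 = 9.1% instead of 8.3%.

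**Step 6. How often?** Neither the missing-PK rate nor the treatment-induced rate is in the documents. If 5% to 10% of pre-dose PK values were missing, that is 0.05 × 18 = 0.9 to 0.10 × 18 = 1.8 participants. If 5% to 20% of participants were treatment-induced, independently of missingness, the expected number of lost cases is 18 × 0.05 × 0.05 = 0.05 to 18 × 0.10 × 0.20 = 0.36 across both cohorts.

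**The case against.** The case on the other side is about scope, and most of it stands.

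- A reader might infer that every participant with a missing pre-dose PK value is misclassified. The definitions do not support that: the three groups in Step 3 are unaffected, and only two patterns change.
- A missed draw would normally lose both results. The IG sample is then unevaluable, and no wording on PK can rescue it.
- A reader might infer that a true treatment-induced case necessarily drops out of ADA incidence, or that incidence is biased downwards. Neither document gives a numerator or denominator. Loss from the treatment-induced class is certain; loss from incidence depends on how incidence is built, and the direction of any bias depends on the denominator.
- The endpoint is descriptive, no decision rests on it, and the expansion was not opened. Sample and participant ADA status are both listed, with titers for positive samples, so a later positive would be visible.

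None of this makes the rule correct for a pre-dose sample. It makes the consequence small and uncommon. The missing-PK rule is sound after dosing, where interference cannot be excluded.

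**Conclusion.** The point holds as a minor defect of definition. For a sample taken before the first sabatolimab infusion, SAP 2.6.4.1 gives the wrong class when the assay is negative and the PK value is absent. Two participant patterns then become Inconclusive wrongly. The 8.3 and 16.7 percentage points show what a single lost case would mean in cohorts of about 12 and 6; they are not expected losses, which stay below one case under every rate assumed above.

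The conclusion assumes that the Cycle 1 Day 8 pre-infusion sample is the ADA baseline. The SAP does not say so. Its general safety baseline (Section 4) must fall no later than the start of any study drug, and azacitidine and venetoclax start on Cycle 1 Day 1. Read literally, that excludes the first IG sample marked in Table 8-9. The Day 1 row of that table is blank in the public copy, possibly through redaction, so no conclusion is drawn from it.

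**What to change.** Add to SAP 2.6.4.1: *An assay-negative sample taken before the first sabatolimab infusion is ADA-negative whether or not a PK value is available; the ADA baseline is the last IG sample before the first sabatolimab infusion.*

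Both halves are needed. The first corrects the class. The second ensures that the Day 8 pre-infusion sample can serve as baseline; otherwise the first may have no effect. Do not set the missing concentration to zero: that would contradict the no-imputation rule in SAP 2.6.3.1 and is unnecessary. Keep the missing-PK rule unchanged for post-dose samples. It would also help to state the numerator and denominator of ADA incidence, including where Inconclusive participants go.

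The cost is one sentence and about one line of programming for the class, with no new data.
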